**CONFIDENTIAL**

Date: 15 February 2022 **Novo Nordisk**  
 Version: 3.0  
 Status: Final  
 Page: 30 of 53

### **9.7.2.2 Analysis of secondary endpoint(s)**

Analyses in the following specific populations of patients will be conducted: Females on oral oestrogen therapy; Adult-onset GHD; Childhood-onset GHD, transition phase from 18 to 25 years and patients switching from daily or other weekly GH treatment after the time of enrolment in the study. Results will be reported separately for treatment-naïve and prevalent users of GH replacement therapy.

Stratified analyses will be performed according to the IGF-I levels (IGF-I SDS [-2, 0], [0, +2] and >+2) at baseline.

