Therefore, as part of the risk management plan for Sogroya® (somapacitan) as treatment of AGHD, the primary aim of this NIS is to characterise the long-term safety profile of Sogroya® (somapacitan) with special focus on the important potential risks (diabetes mellitus type 2, neoplasms and medication errors) and additional long-term safety information. Therefore, this PASS may allow a further evaluation of these potential risks in relation to treatment with Sogroya®. Medication errors are of specific interest since some patients will switch from daily GH injections to weekly injections with Sogroya®. Therefore, the PASS may provide information on whether this might lead to medication errors in clinical practice.

The secondary aim is to investigate the clinical parameters in patients treated with Sogroya® (somapacitan) on body composition, metabolic parameters, skeletal integrity, and quality of life. Clinical parameters will be analysed in specific sub-populations of AGHD patients, defined in protocol section [9.7.2.2](#) as these sub-populations have different starting doses of Sogroya® (somapacitan).

Protocol  
 Study ID: NN8640-4515  
 UTN: U1111-1264-8642  
 EU PAS No: Pending

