### 9.1.1.2 Secondary endpoints

#### 9.1.1.2.1 Safety

Endpoint title	Time frame	Unit
Number of Adverse Events (AEs)	From baseline (week 0) to end of study*	Count
Number of Serious Adverse Events (SAEs)	From baseline (week 0) to end of study*	Count
Number of Medication Errors (incorrect dose administration rate)	From baseline (week 0) to end of study*	Count

\*End of study will differ from patient to patient, but can be between 1 week and a maximum of 10 years

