### 9.2.4 Rationale for selection criteria

The study population is comprised of adult patients diagnosed with GHD and treated with commercially available Sogroya® (somapacitan). The study population will include patients naïve and non-naïve to any GH replacement therapy (including Sogroya® (somapacitan)) at time of study enrolment and will also include patients with severe hepatic impairment, patients with New York

Protocol  
 Study ID: NN8640-4515  
 UTN: U1111-1264-8642  
 EU PAS No: Pending

CONFIDENTIAL

Date: 15 February 2022  
 Version: 3.0  
 Status: Final  
 Page: 20 of 53

Novo Nordisk

Heart Association class 2 heart failure and woman on oral oestrogen treatment who are diagnosed with AGHD.

The few inclusion and exclusion criteria of this study will greatly reduce selection bias. As a multicentre, multinational population has been selected the generalizability of the study is evaluated as high. The study is global and can include all ethnic groups.

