### 9.7.2 Statistical methods

#### 9.7.2.1 Analysis of primary endpoints

The primary endpoints are the number of Adverse Drug Reactions (ADRs), incident neoplasms, and incident T2D from baseline (week 0) up to end of study (week 520).

Frequencies of ADRs during the study period will be summarised by MedDRA SOC and PT. This summary is displayed with number and proportion of patients with at least one event, number of event and event rate (events per 100 patient-years of exposure).

The primary objective of the study is to evaluate safety of once weekly dosing of Sogroya® (somapacitan) in AGHD patients over a study period up to 10 years, and analysis of ADRs will be one of the tools for achieving this. Adverse drug reactions will be analysed using descriptive statistics based on the ‘on treatment’ observation period (primary evaluation) and ‘in-study’ observation period (secondary evaluation) within the study period. The ADRs will be summarised by treatment, MedDRA (Medical Dictionary for Regulatory Activities) system organ class and MedDRA preferred term. The descriptive statistics will include the number and percentage of patients who experienced ADRs, the number of events and rate per 100 person years. ADRs will be listed by treatment and patient with information on severity, relationship to study product and demographics. ADRs with onset before first dosing will be reported in a separate listing.

In addition, incidence rates will be calculated for the endpoints Neoplasm and Diabetes Mellitus type 2.

Results will be reported separately for treatment-naïve and prevalent users of GH replacement therapy, and patients with a history of neoplasia and diabetes mellitus 2 will be addressed in stratified analyses.

For historical reference the primary evaluation, i.e. the on-treatment analysis, will be compared to the same results reported from the Nordinet® IOS database. It is not expected that there will be big differences in the baseline characteristics between the Nordinet® adult population and the population investigated in this study. If there are big differences between baseline characteristics, a matching procedure will be considered when making the comparison. In addition, a sensitivity analysis will be performed, restricting the primary evaluation to a European population only.

Protocol  
 Study ID: NN8640-4515  
 UTN: U1111-1264-8642  
 EU PAS No: Pending

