# 11 Management and reporting of adverse events/adverse reactions

## 11.1 Collection of adverse events and other safety information

Safety definitions and a guideline for evaluation of outcome, severity and causality can be found in [Appendix A](#).

All adverse events including all fatal outcomes on Sogroya® (somapacitan) which occur after informed consent is obtained and until the end of study for each participating patient must be collected and reported to Novo Nordisk.

If the physician becomes aware of events of overdose, abuse, misuse, medication errors, lack of therapeutic effect or occupational exposure related to the study product treatment with or without an associated suspected adverse reaction, this should be reported to Novo Nordisk on the NIS Safety Form and on the medication error, misuse and abuse form (misadministration). These events will be summarised by Novo Nordisk in the interim and final study reports.

For female patients: Pregnancies and pregnancy outcome should be collected including **adverse events** in the pregnant patient, foetus or newborn infant from birth to 12 months of age.

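### No planned analysis separates daily-to-weekly switchers, or the period just after the switch, although that switch is the stated reason for interest in medication errors

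*Protocol*

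**What the plan says.** Protocol section 7 (and 4.3) lists medication errors among the important potential risks and gives the reason: "Medication errors are of specific interest since some patients will switch from daily GH injections to weekly injections". It adds that "the PASS may provide information on whether this might lead to medication errors in clinical practice". Section 9.1.1.2.1 makes the number of medication errors a secondary safety endpoint, counted from baseline to the end of each patient's study, which may be anything from 1 week to 10 years.

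Two patient groupings bear on the question:

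- **Switch subgroup (9.7.2.2):** "patients switching from daily or other weekly GH treatment after the time of enrolment in the study".
- **Naive/prevalent split (9.7.2.1, repeated in 9.7.2.2):** "Results will be reported separately for treatment-naïve and prevalent users of GH replacement therapy". Section 9.2.4 states that "The study population will include patients naïve and non-naïve to any GH replacement therapy", and the same sentence counts Sogroya itself as GH therapy for this purpose.

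For count endpoints, 9.7.2.2 applies the method of the primary endpoint. Under 9.7.2.1 that means the number and percentage of patients, the number of events and a rate per 100 person-years, for the on-treatment and in-study periods. Time since start appears elsewhere: continuous secondary endpoints (9.7.2.2) and the number of anti-diabetic medications (9.7.2.3) are to be shown by duration of follow-up and of treatment. No such breakdown is stated for medication errors.

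**The concern.** The exposure behind the question is a change in injection frequency, and errors caused by an unfamiliar schedule would be expected mostly soon after the change. The planned groupings are not built around that exposure. Patients from another weekly product share a subgroup with those from daily GH. Patients long settled on Sogroya can share a stratum with those who have just switched. A single rate over years of steady use then outweighs the first months. If there is an early excess among daily-to-weekly switchers, the planned tables could show little of it, on a risk that the protocol names as one of its reasons for doing the study.

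**Working it through.** **Plan's own figures.** The protocol gives no medication-error rate, no expected share of switchers and no transition window. Its only sizing figure concerns neoplasm: section 9.5, Table 1 gives 0.9–3.9% for 400 patients at 2%. The exact binomial interval for 8/400 is 0.87–3.90%, so that entry reproduces, but it does not bear on this endpoint.

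**Who is in each group**

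| Patient | Switch subgroup | Naive/prevalent split |
|---|---|---|
| Daily GH to Sogroya after enrolment | in | prevalent |
| Other weekly GH to Sogroya after enrolment | in | prevalent |
| Daily GH to Sogroya shortly before enrolment | out | prevalent |
| Established Sogroya user at enrolment | out | prevalent |
| Never on GH | out | naive |

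The prevalent column reads the split with the definition in 9.2.4, since 9.7.2 does not define the strata itself. Neither grouping contains daily-to-weekly switchers alone. Established users affect the prevalent stratum only.

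**Time.** The on-treatment and in-study periods in 9.7.1 both run from first administration to the end of observation or treatment. The interim reports (9.7.3) repeat the same approach at data cuts 3 and 6 years after the first patient's first visit. These are calendar cuts and do not separate time since switch.

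**Size of the dilution (all inputs assumed).** Let RR be the rate ratio during a window of w years after the switch, T the average follow-up, and s the share of the group's person-time from daily-to-weekly switchers, with everyone else at the base rate:

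apparent ratio = 1 + s × (RR − 1) × w / T

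*Illustration 1:* 40 errors per 100 patient-years for the first 3 months, 4 per 100 afterwards (RR = 10, w = 0.25), T = 5, s = 1.
- Average rate = (0.25 × 40 + 4.75 × 4) / 5 = 29 / 5 = 5.8 per 100
- Ratio = 5.8 / 4 = 1.45

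*Illustration 2:* RR = 5, w = 0.5.

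| | T = 5 | T = 7.5 | T = 10 |
|---|---|---|---|
| s = 1 | 1 + 4 × 0.5/5 = 1.40 | 1.27 | 1.20 |
| s = 0.5 | 1.20 | 1.13 | 1.10 |

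*Pooling alone, looking only inside the window (RR = 5):* at s = 0.9, 1 + 0.9 × 4 = 4.6; at s = 0.5, 3.0.

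*Range:* with RR 3–10, w 3–12 months, T 5–10 years and s 0.25–1, the apparent ratio runs from 1 + 0.25 × 2 × 0.25/10 = 1.01 to 1 + 9 × 1/5 = 2.80.

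In these examples, averaging over the whole period does most of the damage. Pooling adds to it, and adds little if few patients come from another weekly product.

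**The case against.** The protocol promises only that the study may provide information. Medication errors are a secondary endpoint, the primary objective does not name them, the ENCePP checklist marks hypotheses as not applicable, and the analysis is descriptive. A reader might infer that the plan was meant to show whether switching causes errors and fails, or that the report would conclude that switching is harmless. The documents support neither: a single-arm observational study could not establish cause, and no planned contrast would yield that conclusion.

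A reader might also infer that established users dilute the switch subgroup. They do not, because it is limited to switches after enrolment. That limit is itself defensible: safety data start at consent, so the early period of someone who switched earlier is partly or wholly unobserved.

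Nor do the documents support calling data capture purely passive. Section 11.1 does rely on the physician becoming aware of an error. But section 11.3 requires an event-specific form regardless of seriousness, section 9.2.6.2 has patients asked about adverse events at each contact, suggesting an open question about problems, and the flow chart schedules dosing and titration at every visit after baseline.

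Finally, time bands could be left to a statistical analysis plan. That stands in part, since nothing forbids them there. But the protocol itself fixes the pooled subgroup and the whole-period summary for this endpoint, and specifies time breakdowns for other endpoints. An analysis plan that simply follows it would inherit the problem.

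**Conclusion.** The concern holds in a limited form. The protocol ties its interest in medication errors to the daily-to-weekly switch, yet no planned analysis isolates those patients or the period just after the change. An excess confined to that period would be diluted, chiefly by averaging over up to 10 years and secondarily by mixing patient types. The size cannot be fixed from the document. Under the assumptions shown, a 5- to 10-fold early excess would typically read as about 1.1- to 1.5-fold, and the wider range examined gives 1.01 to 2.80. This is a weakness in how a descriptive secondary analysis is cut. It does not affect the primary endpoints, and it does not show that the study can say nothing about medication errors.

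**What to change.** In section 9.7.2.2, for medication errors, report separately:

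- (a) GH-naive starters;
- (b) patients switching from daily GH;
- (c) patients switching from another weekly GH;
- (d) patients already on Sogroya at enrolment.

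Within these groups give the rate by time since first Sogroya dose, for example 0–3, 3–12 and more than 12 months, counting only events and person-time after consent. Keep the bands coarse and descriptive, and report the prior regimen as unknown where it is not available.

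The cost is wording and one or two tables. Much of the data is already collected: previous GH treatment (9.2.8.6), Sogroya dosing at entry (9.2.8.8) and the medication-error form (11.3). Two limits should be stated. The retrospective data cover 12 months and only where available, so the prior regimen and first-dose date are not assured for longer-term Sogroya users. The strata will also be small: 4 groups by 3 bands is 12 cells from 400 patients. If, say, 100 patients switched from daily GH, the first 3 months would supply at most 100 × 0.25 = 25 patient-years, so intervals will be wide.

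A direct prompt about extra or wrong-day injections could be added to the existing missed-dose question. It is optional and not part of the defect.

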**Novo Nordisk**

Additionally, the severity of GH deficiency expressed as IGF-I SDS level prior to any initiation of GH treatment should be collected at baseline, if available.

Data on the number of patients with a minimum of 1-year of follow-up achieving the age-adjusted IGF-I SDS levels up to the upper limit of the normal reference range (0 and +2) will be reported (i) as part of the progress reports in connection with the PSURs - as soon as first data are available and (ii) as part of the interim reporting (data cut 3 and 6 years after FPFV).

Monitoring of safety in this study will be performed from time of enrolment, defined by signing of the informed consent, until the patient's last visit in the study (defined as end of study or withdrawal of informed consent). Adverse events are expected to be captured and reported by the participating sites during routine clinical evaluations (expected every 6-12 months) and any other intermediate contacts with the patient (e.g. phone call etc).

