### 9.2.2 Inclusion criteria

For an eligible patient, all inclusion criteria must be answered “yes”.

1. Signed consent obtained before any study-related activities (study-related activities are any procedure related to recording of data according to the protocol).
2. The decision to initiate treatment with commercially available Sogroya® (somapacitan) has been made by the patient and the treating physician before and independently from the decision to include the patient in this study.
3. Male or female, age above or equal to 18 years assigned to Sogroya® (somapacitan) treatment at the time of signing informed consent.
4. Diagnosis of adult growth hormone deficiency (AGHD) as per local practice

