### 9.2.7.5 Biomarkers

Samples obtained from local laboratory in accordance with normal clinical practice should be recorded in the eCRF if available:

- IGF-I
- IGFBP-3
- IGF-I standard deviation score (SDS)

Local Assay method and reference ranges must be collected and shared with Novo Nordisk.

Data obtained a maximum of 6 months before informed consent is signed can be used for baseline data if evaluated still to be valid by the physician. If more than one previously obtained data is available, the latest one should be used.

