**Novo Nordisk**

### **Categorical secondary endpoints:**

The binary categorisation of the endpoints Patient achieving IGF-I SDS target (0 -+2) and Patient reaching satisfactory clinical response will be used to calculate the proportion (%) of patients achieving these criteria.

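### The baseline IGF-I strata in section 9.7.2.2 have no place for patients below -2 SDS and count a value of exactly 0 twice

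*Protocol*

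**What the plan says.** Protocol section 9.7.2.2, ahead of the lists of count, continuous and categorical secondary endpoints, fixes the cut-points: the analyses are to be stratified "according to the IGF-I levels (IGF-I SDS [-2, 0], [0, +2] and >+2) at baseline". The sentence just before it adds a second split: "Results will be reported separately for treatment-naïve and prevalent users of GH replacement therapy".

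Four other places bear on who can fall where:

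- Section 9.2.2 admits patients on "Diagnosis of adult growth hormone deficiency (AGHD) as per local practice". Neither the inclusion nor the exclusion criteria mention an IGF-I limit.
- Section 9.2.4: "The study population will include patients naïve and non-naïve to any GH replacement therapy", the latter including patients already on somapacitan.
- Section 9.2.7.5, on the biomarkers: "Data obtained a maximum of 6 months before informed consent is signed can be used for baseline data". The latest such value is used, and IGF-I is recorded only where it is available.
- Section 9.1 asks that "the severity of GH deficiency expressed as IGF-I SDS level prior to any initiation of GH treatment should be collected at baseline", if available. IGF-I SDS is thus the protocol's own scale of severity.

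No section adds a stratum below -2 or says which stratum takes a value of 0.

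**The concern.** A set of strata should place each patient with a baseline value in exactly one group. Here the lowest interval starts at -2, the bottom of a -2 to +2 range, in a study of a disease that lowers IGF-I. For a GH-naive patient the baseline value can be a pre-treatment one, so a value below -2 marks the most severe deficiency on the scale that section 9.1 adopts. That group has no row in the stratified tables.

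If the rule is followed, the stratified results for adverse events, serious adverse events, medication errors and the continuous endpoints say nothing about these patients, and the stratum counts fall short of the number with a baseline IGF-I. Section 9.7.3 has the interim reports use the same analytic approach as the final report, so the gap would appear at the 3-year and 6-year cuts and again at the end.

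This is not detail left for a statistical analysis plan. The protocol states the cut-points. A plan that follows them inherits the gap, and a plan that repairs them departs from the protocol.

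**Working it through.** **Step 1: coverage check.** This needs no assumption. Values are assigned to the intervals exactly as written, with closed brackets.

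| Baseline SDS | Strata that contain it |
|---|---|
| -4, -3, -2.1 | none |
| -2, -1 | [-2, 0] |
| 0 | [-2, 0] and [0, +2] |
| 1, 2 | [0, +2] |
| 2.1 | >+2 |

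Every value below -2 is unassigned. Only the single point 0 is assigned twice.

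**Step 2: can values below -2 occur?** Entry is by local diagnosis with no IGF-I limit (9.2.2), naive patients are enrolled (9.2.4), and for a naive starter the baseline value may precede treatment (9.2.7.5). Nothing in the protocol rules them out.

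**Step 3: how many?** The protocol states no figure to reproduce. It gives N = 400 (9.2.1) but neither the share of naive patients nor any baseline IGF-I distribution. The rest of this step is therefore an illustration on assumptions: a normal distribution with SD 1.3 in both groups, treated users centred at 0, naive mean between -1.5 and -2.5, and a baseline value for all 400.

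Share below -2 = Φ((-2 - mean)/SD):

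- treated users: Φ(-2/1.3) = 0.062
- naive, mean -1.5: Φ(-0.5/1.3) = 0.350
- naive, mean -2.5: Φ(0.5/1.3) = 0.650

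Unassigned patients = 400 × [f × naive share + (1 - f) × 0.062], where f is the naive fraction:

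| f | Naive mean -1.5 | Naive mean -2.5 | Naive among the unassigned |
|---|---|---|---|
| 10% | 40 × 0.350 + 360 × 0.062 = 36 | 40 × 0.650 + 360 × 0.062 = 48 | 39% to 54% |
| 25% | 100 × 0.350 + 300 × 0.062 = 54 | 100 × 0.650 + 300 × 0.062 = 84 | 65% to 78% |
| 50% | 200 × 0.350 + 200 × 0.062 = 82 | 200 × 0.650 + 200 × 0.062 = 142 | 85% to 91% |

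The naive share itself moves with the assumed mean and SD. With SD 1 to 1.5 it is 16% to 25% at mean -1, 31% to 37% at mean -1.5, and 63% to 69% at mean -2.5. Patients without a recorded baseline IGF-I would lower all the counts.

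**Step 4: the repaired strata.** With < -2, [-2, 0), [0, +2] and > +2, each value in Step 1 falls in exactly one stratum. The third stratum then matches the 0 to +2 target used elsewhere in the protocol.

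**The case against.** The best defence is that little depends on this stratification. It is secondary and descriptive. The ENCePP checklist marks hypothesis testing as not applicable, and the protocol specifies no estimate pooled or adjusted across the IGF-I strata. Each stratum that is printed is correct for its own patients, so the fault is a missing row and not a distorted result. All of that stands, and it limits the weight of the point without removing it.

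The overlap at 0 is only a bracket convention. That stands too.

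The severity argument also needs care. Section 9.1 speaks of IGF-I before any GH treatment, whereas the strata use IGF-I at baseline. The two can coincide for naive patients. For prevalent users the baseline value is taken on treatment and does not measure original severity.

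A reader might infer more than the protocol supports:

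- *That severely deficient patients disappear from the safety results.* They do not. The Safety Analysis Set in 9.7.1 takes all exposed patients; the primary analyses in 9.7.2.1 and the overall secondary summaries use them; and naive and prevalent users are already reported separately.
- *That the unassigned patients are mainly GH-naive.* This holds in most of the scenarios above but not all: with 10% naive and a mean of -1.5, only 39% of them are.
- *That the Yes/No IGF-I endpoint at 12 months is flawed because* No *pools values below 0 with values above +2.* The stated objective is the number achieving 0 to +2, and a proportion answers it. Change in IGF-I SDS is analysed as a continuous endpoint as well. Splitting *No* is a preference.

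**Conclusion.** The point holds in a narrow form. The strata as stated leave a gap below -2 and overlap at 0. Both follow from the text alone and are certain. The gap matters because, among naive patients, it omits the most deficient on the protocol's own scale from the IGF-I-stratified secondary analyses, and only from those. The overlap is minor.

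The size is not known. The range of about 36 to 142 of 400 comes from the assumed naive share (10% to 50%), the assumed means and SD, and complete baseline data. It shows that the gap need not be negligible; it is not a forecast of the loss. No sample size, precision or primary-endpoint figure is affected.

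**What to change.** In section 9.7.2.2, replace the three intervals with four disjoint and exhaustive ones: below -2; -2 to below 0; 0 to +2 inclusive; above +2. Carry the same cut-points into the statistical analysis plan.

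The cost is one line of wording. The data are the same, and neither the sample size nor the planned naive/prevalent reporting changes.

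Optionally, tabulate the 12-month IGF-I result as below 0, 0 to +2 and above +2 beside the Yes/No proportion. This is a suggestion for fuller reporting and does not correct an error in the plan.
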